8.6 Variables

8.6.1. Exposures

Positive test result for SARS-CoV-2

RT-PCR tests have high sensitivity and specificity for SARS-CoV-2. However, as a result of changes in the availability of population wide RT-PCR and home self-reported lateral flow tests during the Omicron period, it may not be possible to exclusively use RT-PCR tests when identifying positive test results in all datasets.[23] All positive test results for SARS-CoV-2 observable in the database will therefore be included for the primary analysis, with documentation of what type of test it was to allow sensitivity analysis restricted to RT-PCR diagnosed patients as needed.

Clinical diagnosis of COVID-19

Whilst testing for SARS-CoV-2 was commonly performed in some of the countries that will be represented in this study, clinical diagnoses of COVID-19 were also made for many individuals. Diagnostic codes compatible with COVID-19 will therefore also be identified, with the recorded date being used in the analyses.

Hospitalisation with COVID-19

Patients hospitalised with COVID-19 will be identified based on having a hospitalisation along with a confirmatory diagnosis or test result of COVID-19 (both as defined above) within a time window from 21 days prior to admission up to three days following their admission. This time window has been chosen to include those who had the diagnosis made prior to their hospitalisation and to allow for a delay in test results or diagnoses to be made or recorded, while excluding individuals with hospital-acquired COVID-19.

Intensive care services during a hospitalisation with COVID-19

Patients who received intensive care services during a hospitalisation with COVID-19 will be identified based on having a hospitalisation where they were admitted to the intensive care unit, received mechanical ventilation, tracheostomy, or extracorporeal membrane oxygenation (ECMO). If the date at which the intervention was initiated is observable in the database, this date will be used as the index date. If the date at which the intervention was initiated is not observed (for example, if such interventions are recorded at time of discharge) then the date of ICU admission, or hospital admission if ICU admission is not recorded, will be used as the index date.

Vaccination against SARS-CoV-2

COVID-19 vaccine exposure will be defined as the date of a vaccination record. Vaccination exposures will be defined by dose (1st, 2nd, 3rd, 4th etc.) and brand. The standard concepts used to define vaccine are available in the appendix.

Table 5. Operational Definitions of Exposure

Exposure group name(s)	Details	Washout window	Assessment Window	Care Setting ¹	Code Type	Diagnosis position ²	Applied to study populations:	Incident with respect to...	Measurement characteristics/validation	Source of algorithm
Positive test result for SARS-CoV-2	All positive test results for SARS-CoV-2 observable in the database. We will record the test type as well.	3 months	n/a	OP, IP	SNOMED	n/a	All meet observation period criteria	n/a	n/a	n/a
Clinical diagnosis of COVID-19	Diagnostic codes compatible with COVID-19 will therefore also be identified	3 months	n/a	OP, IP	SNOMED	n/a	All meet observation period criteria	n/a	n/a	n/a
Covid-19 hospitalization	having a hospitalisation along with a confirmatory diagnosis or test result of COVID-19 (both as defined above) within a time window from 21 days prior to admission up to three days following their admission.	3 months	n/a	IP	SNOMED		All meet observation period criteria	n/a	n/a	n/a
Covid-19 intensive care services	received intensive care services during a hospitalisation with COVID-19 will be identified based on having a hospitalisation where they were admitted to the intensive care unit, received mechanical ventilation,	n/a	During hospitalization	IP	SNOMED	n/a	All patient meet the covid-19 hospitalization criteria	n/a	n/a	n/a

	Phase II C3-001 – Study Protocol	
	Author(s): [name], [name]	Version: v3.1
	Dissemination level: public	

	tracheostomy, or extracorporeal membrane oxygenation (ECMO).									
Vaccination against SARS-CoV-2	COVID-19 vaccine exposure will be defined as the date of a vaccination record. Vaccination exposures will be defined by dose (1 st , 2 nd , 3 rd , 4 th etc.) and brand.	21 days	n/a	OP	SNOMED	n/a		n/a	n/a	n/a

¹ IP = inpatient, OP = outpatient

² Specify whether a diagnosis code is required to be in the primary position (main reason for encounter)

Criterion: A brief text entry naming the in- and/or exclusion criterion (e.g. age, sex, atrial fibrillation)

Details: An optional brief text description to provide more information about the in- and/or exclusion criterion (e.g. age in years defined by (time 0 – year of birth)/365, baseline enrolment measured by Part A, B, D and no HMO insurance coverage with 30 day gaps allowed), 2 codes required

Order of application: Specify whether the in and exclusion criterion is applied before or after selection of the study entry date. For example, enter “before” if you plan to apply the criterion, identify all possible study entry dates, and then choose one or more. Enter “after” if you select the first possible study entry date and then apply the in- and/or exclusion criterion. If the patient does not meet the criterion, then the patient drops out. These decisions can impact which samples of person-time are included in the study.

Assessment window: Use bracketed numbers representing time intervals anchored on a primary anchor (usually time 0) to specify the window over which to evaluate patient data relevant for the in- and/or exclusion criterion. For example, [-180, 0] would reflect an assessment window of 180 days prior to and including time 0, where the brackets indicate that the window is inclusive of the endpoints.

Care setting: Specify the care setting(s) that are used in the algorithm to define the in- and/or exclusion criterion. For example, IP = inpatient, ED = emergency department, etc.

Code type: Specify the type(s) of clinical codes that are used to define the in- and/or exclusion criterion.

Diagnosis position: If the algorithm to define the in- and/or exclusion criterion used inpatient codes, specify whether the algorithm restricts to primary diagnosis codes (indicating that the code is the primary reason for the encounter) or allows codes in secondary or any position (e.g. primary, secondary, any, n/a)

	Phase II C3-001 – Study Protocol	
	Author(s): [name], [name]	Version: v3.1
		Dissemination level: public

Applied to study populations: Indicate which study populations the in- and/or exclusion criterion should be applied to (study population names are specified in Table 2).

Measurement characteristics/validation: If there are measurement characteristics for the outcome algorithm (e.g. PPV, sensitivity, specificity) from publications, or from outcome validation within the study population (e.g., medical record review), provide this information.

Source of algorithm: Specify the source of algorithms to define the in- and/or exclusion criterion.

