8.4 Follow-up

For cohort 1, follow-up will begin on January 1st 2017 and continue up until the first of: outcome of interest, loss to follow-up, death or December 31st 2019. For cohorts 2 to 5, follow-up will begin on their index date and continue up until the first of: outcome of interest, end of observation period, end of data availability, death, or either 30-, 60-, 90- or 180-days after the index date (depending upon the follow-up time period of interest).

Table 2: Operational Definition of Time 0 (index date) and other primary time anchors

Study population name(s)	Time Anchor Description (e.g. time 0)	Number of entries	Type of entry	Washout window	Care Setting ¹	Code Type	Diagnosis position	Incident with respect to...	Measurement characteristics / validation	Source of algorithm
Background population (cohort 1*)	January 1 st 2017 or after when they have 365 days of prior history	Multiple	General population	n/a	n/a	n/a	n/a	n/a	n/a	n/a
SARS-CoV-2 infection cohort (cohort 2*)	Date of test for the positive test result for SARS-CoV-2, or date of clinical diagnosis of COVID-19	Multiple	incident	No covid-19 infection within 3 months prior	OP	SNOMED codes (see appendix)				
hospitalised with COVID-19 cohort (cohort 3*)	Date the date of hospital admission	Multiple	incident	No hospitalization within	IP	SNOMED codes (see appendix)				

This document represents the views of the DARWIN EU® Coordination Centre only and cannot be interpreted as reflecting those of the European Medicines Agency or the European Medicines Regulatory Network.

	Phase II C3-001 – Study Protocol	
	Author(s): [name], [name]	Version: v3.1
	Dissemination level: public	

				3 month s prior						
Intensive care service cohort (cohort 4*)	Date of the following depends on availability in data, descend priority: 1.)Date of intensive care service (mechanical ventilation, tracheostomy, or extracorporeal membrane oxygenation (ECMO)); 2.)Date of ICU admission; 3.)Date of hospital admission.	Multiple	incident	n/a	IP	SNOMED (see appendix)	n/a	Covid-19 hospitalized	n/a	n/a
Vaccinated cohort (cohort 5*)	date of vaccination record	Multiple	n/a	21 days	OP	RxNorm codes (see appendix)				

*Cohorts number as described in 8.5 study population with inclusion and exclusion criteria.

¹ IP = inpatient, OP = outpatient, ED = emergency department, OT = other, n/a = not applicable

Description of the different items from the table can be found below:

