8.5 Study Population with inclusion and exclusion criteria

Five non-mutually exclusive study cohorts for the analyses will be defined:

- 1. General population cohort for pre-pandemic background rates** will have
 - Individuals will start contributing as of 1st January 2017, or when they have at least 365 days of data availability.
 - follow-up for this cohort will run up to 31 December 2019.
- 2. Persons tested positive for SARS-CoV-2 or with a clinical diagnosis of COVID-19 during the Omicron period** will
 - have either a positive test result for SARS-CoV-2 or a clinical diagnosis of COVID-19 on or after 1st December 2021 (with the index date being whichever date comes first if both occur)
 - have no positive test result for SARS-CoV-2 or clinical diagnosis of COVID-19 within 3 months prior to the index date.
 - have at least 365 days of data availability prior to index date
- 3. Persons hospitalised with COVID-19 during the Omicron period** will have
 - a hospitalisation on or after 1st December 2021 (with the index date the date of hospital admission),
 - a record of a clinical diagnosis of COVID-19 or a positive test result for SARS-CoV-2 in the period between 3 weeks prior to and up to 3 days following the index date.
 - have no diagnosis of COVID-19 or a positive test result for SARS-CoV-2 between 3 months and 3 weeks prior to index date.
 - have no COVID-19 hospitalisation within 3 weeks prior to the index date.
 - have at least 365 days of data availability prior to index date
- 4. Persons requiring intensive services during a hospitalisation with COVID-19 during the Omicron period** will have
 - intensive services initiated during a hospitalisation as described in cohort 3 (with the index date the date at which intensive services were initiated)
 - patients will have had a confirmatory diagnosis or test result of COVID-19 (both as defined above) within a time window from 3 weeks to their index date up to three days following their index date.
 - have at least 365 days of data availability prior to index date
- 5. Persons vaccinated against SARS-CoV2 infection**
 - a vaccination record identified by brand (with the index date the date of vaccination record)

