Covid-19 intensive care use (cohort 4)	intensive services initiated during a hospitalisation as described in the “covid-19 hospitalized” criterion	before	During hospitalization	Intensive care	SNOMED	n/a	Individuals who met the “covid-19 hospitalized” criteria	n/a	n/a
Covid-19 vaccinated (cohort 5)	a vaccination record identified by brand (with the index date the date of vaccination record)	before	n/a	Primary care	RxNorm	n/a	All individuals within the selected databases	n/a	n/a

¹ IP = inpatient, OP = outpatient, ED = emergency department, OT = other, n/a = not applicable

² Specify whether a diagnosis code is required to be in the primary position (main reason for encounter)

Table 4. Operational Definitions of Exclusion Criteria

Criterion	Details	Order of application	Assessment window	Care Setting¹	Code Type	Diagnosis position²	Applied to study population^s	Measurement characteristic^{s/}	Source for algorithm
Prior covid-19 (cohort 2-4)	have no positive test result for SARS-CoV-2 or clinical diagnosis of COVID-19 within 3 months prior to the index date.	After	[-91,0]	OP,IP	SNOMED, RxNorm	n/a	SARS-CoV-2 infected, hospitalized (cohorts 2, 3, 4)	n/a	n/a

	Phase II C3-001 – Study Protocol	
	Author(s): [name], [name]	Version: v3.1
	Dissemination level: public	

Hospitalization (cohort 3)	have no diagnosis of COVID-19 or a positive test result for SARS-CoV-2 between 3 months and 3 weeks prior to index date. Have no COVID-19 hospitalisation within 3 weeks prior to the index date.	After	Covid-19 [-91,-21]; Hospitalization [-21,0]	IP	SNOMED	n/a	Covid-19 hospitalized (cohorts 3, 4)	n/a	n/a
Vaccinated (cohort 5)	No vaccine records in the 21 days prior to index vaccine	after	[-21 , 0]	OP	RxNorm	n/a	Vaccinated (cohort 5)	n/a	n/a
Prior outcomes all cohorts)	Exclude people with the outcome of interests during the 183 day prior to index. (primary analysis, different washout period will be applied in sensitivity analysis)		[-183,0]	IP, OP	SNOMED	n/a	(cohorts 1-5)	n/a	n/a

1 IP = inpatient, OP = outpatient, ED = emergency department, OT = other, n/a = not applicable

2 Specify whether a diagnosis code is required to be in the primary position (main reason for encounter)

Criterion: A brief text entry naming the in- and/or exclusion criterion (e.g. age, sex, atrial fibrillation)

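### The intensive-care cohort (cohort 4) has no single time origin: a later ventilation date overrides a recorded ICU admission, and hospital admission is allowed as a fallback

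*Protocol*

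**What the plan says.** Section 8.6.1 places in cohort 4 any patient hospitalised with COVID-19 who was "admitted to the intensive care unit, received mechanical ventilation, tracheostomy, or extracorporeal membrane oxygenation (ECMO"). Any one of these is enough, so ICU admission without organ support qualifies.

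The index date is then fixed in three places:

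- **Section 8.5, cohort 4:** "with the index date the date at which intensive services were initiated". No fallback is given.
- **Section 8.6.1:** "If the date at which the intervention was initiated is observable in the database, this date will be used as the index date". If it is not observed, "then the date of ICU admission, or hospital admission if ICU admission is not recorded, will be used as the index date".
- **Table 2 (section 8.4):** "Date of the following depends on availability in data, descend priority". The date of ventilation, tracheostomy or ECMO ranks first, followed by "2.)Date of ICU admission; 3.)Date of hospital admission".

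Section 8.4 starts follow-up for cohorts 2 to 5 at the index date and runs it for 30, 60, 90 or 180 days. Table 4 applies this rule to all five cohorts, with window [-183,0]: "Exclude people with the outcome of interests during the 183 day prior to index".

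**The concern.** The ranking follows what is recorded and which service was given, not the first moment at which the patient qualified. Two things follow.

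First, a patient who is admitted to ICU and ventilated some days later qualified at ICU admission but starts follow-up at ventilation. An unventilated patient starts at ICU admission. Day 0 therefore means different things within one cohort, and the days just after ICU admission are missing for the ventilated patients only.

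Second, a patient indexed at hospital admission belongs to cohort 4 only because intensive care came later. Follow-up then begins before the patient qualified.

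The analyses at stake are cohort 4 incidence and the 90-day cumulative incidence with death as competing event (8.8.2), the Cox models fitted to each COVID-19 cohort (8.8.3), and any ratios to background computed for cohort 4 (8.8.5). The transitions listed in 8.8.4 contain no ICU state and are not directly affected.

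**Working it through.** The protocol gives no event count, precision or date-completeness figure for cohort 4, so there is no stated number to reproduce. The rules can be followed through, and the rest is illustration.

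**1. The rules side by side**

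| Patient | Qualifies at | Index date (Table 2) | Consequence |
|---|---|---|---|
| ICU, never ventilated | ICU admission | ICU admission | Origin matches qualification |
| ICU, ventilated later, both dates recorded | ICU admission | Ventilation | A VTE/ATE between the two dates precedes the index date; Table 4 excludes the patient |
| Neither intervention nor ICU date recorded | Unknown later day | Hospital admission | Ward days counted as follow-up; no death possible in them; ward VTE/ATE counted as intensive-care events |

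The second row needs no missing data; it arises with complete recording. Table 6 ends its outcome washout at day -1 and Table 4 at day 0, but an event on a day before ventilation falls inside both windows. The index date also anchors the cohort 4 COVID-19 confirmation window (8.5) and the pre- and post-index medication windows (8.6.3), so these shift with it.

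**2. Patients excluded by the ventilation-first rule (illustration)**

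Section 6 cites a 31% incidence of thrombotic complications in an early-pandemic ICU case series, without an accrual time. Assume it accrues at a constant hazard over D days: h = -ln(1 - 0.31)/D. The share with an event during a gap of g days is 1 - exp(-h × g).

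| D (days) | h per day | g = 1 | g = 2 | g = 5 |
|---|---|---|---|---|
| 7 | 0.0530 | 5.2% | 10.1% | 23.3% |
| 14 | 0.0265 | 2.6% | 5.2% | 12.4% |
| 30 | 0.0124 | 1.2% | 2.4% | 6.0% |

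These are shares of patients ventilated g days after ICU admission, not of the whole cohort.

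**3. Ward time under the hospital-admission fallback (illustration)**

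For a patient indexed at admission with a lag of L days to ICU, the ward share of the follow-up window is L/window.

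| L (days) | 30-day | 90-day | 180-day |
|---|---|---|---|
| 1 | 3.3% | 1.1% | 0.6% |
| 3 | 10.0% | 3.3% | 1.7% |
| 5 | 16.7% | 5.6% | 2.8% |
| 10 | 33.3% | 11.1% | 5.6% |

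This is a share of time for that patient. It is not a bias in the rate.

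**4. Same patients, three index rules (simulation, 1,000,000 patients per setting)**

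Assumptions: exponential lag from hospital to ICU and exponential gap from ICU to ventilation; every patient is ventilated; no death before ventilation, then 0.01 per day. In the peaked setting the VTE/ATE hazard is 0.002 per day on the ward, 0.0265 for 14 days from ICU admission, then 0.002. In the flat setting it is 0.01 throughout. Patients with an event before index are excluded. Cells give the result for hospital / ICU / ventilation index.

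| Setting | 30-day events per 1000 person-days | Excluded | 30-day deaths |
|---|---|---|---|
| Peaked, mean lag 4, mean gap 2 | 14.37 / 15.59 / 13.78 | 0 / 0.8% / 5.8% | 21.2% / 24.4% / 25.9% |
| Peaked, mean lag 7, mean gap 3 | 13.35 / 15.62 / 12.95 | 0 / 1.4% / 8.6% | 18.2% / 23.7% / 26.1% |
| Flat, mean lag 4, mean gap 2 | 9.97 / 9.98 / 9.99 | 0 / 3.8% / 5.7% | 21.3% / 24.4% / 25.9% |

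Relative to the ICU index, the peaked settings give 14.37/15.59 - 1 = -7.8% and 13.78/15.59 - 1 = -11.6%, then 13.35/15.62 - 1 = -14.5% and 12.95/15.62 - 1 = -17.1%. With a flat hazard the event rates agree, while the death proportions still differ.

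**The case against.** **The fallback may never be used.** Section 8.6.1 words part of the rule at database level, as a provision for a network, and only SIDIAP has inpatient data. Nothing shows that SIDIAP lacks ICU dates for any patient. Section 11 adds that only cohorts that can be reliably identified will be analysed. This stands: a mixture of three origins is possible under the text but not shown to occur. It does not touch the ventilation-over-ICU ranking, which operates when every date is present.

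**Section 8.5 gives the target and 8.6.1 the substitute.** That is a fair reading of how the text came about. Even so, hospital admission is not the start of intensive services; it is the index date of cohort 3. Section 8.5 does not say that a substitute is allowed.

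**Removing events before index is what a washout does, and they are not lost to the study.** The cohorts overlap, and a thrombosis between ICU admission and ventilation falls after the cohort 3 index date and counts there. This is correct. The loss is confined to cohort 4, where it falls only on patients ventilated after they had already qualified.

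**Stronger readings a reader might infer.** One is classic immortal-time bias in the VTE/ATE rates. The documents do not support this: the ward interval is immortal for death, and so for fatal events and the competing risk, but a non-fatal VTE or ATE in it is counted. Another is that the two departures bias the incidence in opposite directions. In the peaked simulations both lower the rate, and with a flat hazard neither changes it; only the death proportions move in opposite directions.

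**Conclusion.** The point holds as an inconsistency in the definition of time zero. Under sections 8.4 and 8.6.1, ventilated and unventilated cohort 4 patients start follow-up at different points of the same clinical course. With Table 4, a VTE or ATE between ICU admission and ventilation takes the patient and the event out of cohort 4. This follows from the text alone. No sensitivity analysis in Table 9 varies this date.

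The hospital-admission fallback is a conditional second point. It contradicts 8.5 and would start follow-up before qualification, but the number of patients affected in SIDIAP is unknown and may be zero.

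Neither the direction nor the size of the effect on the VTE/ATE rate can be derived from the protocol. The illustrative shifts of about 8% to 17% rest on assumed lags, gaps and a hazard peaking after ICU admission; they vanish under a constant hazard. The 31% behind the peaked hazard comes from an early-pandemic series and may not apply to Omicron. To call the cohort 4 rates uninterpretable would go beyond this. They would describe a mixed time origin, which one aligned definition removes.

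**What to change.** Set the cohort 4 index date to the earliest recorded date of ICU admission or any qualifying intensive service (ventilation, tracheostomy, ECMO), and state it identically in section 8.5, section 8.6.1 and Table 2. This date is the first at which a patient is known to qualify, and it agrees with 8.5.

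Report how many patients have only a hospital-admission date. Leave them out of the main cohort 4 analysis and add them back in a sensitivity analysis, entered in Table 9.

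The change needs no new data. Section 5 still lists creation of the analytical code as to be confirmed. The COVID-19 confirmation and medication windows anchored on the index date move with it and should be checked. The downside is a possible small loss of patients from the main analysis in the one database with inpatient data.

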8.6.2. Outcomes

Venous thromboembolic events

In the primary analysis, venous thromboembolic events will be identified by diagnostic codes for pulmonary embolism or deep vein thrombosis. In a secondary analysis pulmonary embolism and deep vein thrombosis will be assessed separately. We will also assess portal vein thrombosis, splanchnic venous thrombosis (SVT) and cerebral venous sinus thrombosis separately.

Arterial thromboembolic events

In the primary analysis, arterial thromboembolic events will be identified by an acute myocardial infarction or acute ischemic stroke. In a secondary analysis acute myocardial infarction and acute ischemic stroke will be assessed separately. We also identify stroke in general, for which we will include both ischemic, haemorrhagic and non-specifically recorded stroke.

Cardiovascular events

Instances of heart failure, cardiac arrhythmia, and angina will be identified. In addition, major cardiovascular events (MACE) will be identified by heart failure, acute myocardial infarction, or stroke, or the occurrence of sudden cardiac death. As a sensitivity analysis, we will require that events were identified by hospitalisation admission or discharge records.

Table 6. Operational Definitions of Outcome

Outcome name	Details	Primary outcome?	Type of outcome	Washout window	Care Settings ¹	Code Type	Diagnosis Position ²	Applied to study:	Measurement characteristics/validation	Source of algorithm
Venous thromboembolic events	venous thromboembolic events will be identified by diagnostic codes for pulmonary embolism or deep vein thrombosis	Yes	Binary, time-to-event	[-183,-1]	IP,OP	SNOMED	n/a	All included cohorts	n/a	n/a
Arterial thromboembolic events	arterial thromboembolic events will be identified by an acute myocardial infarction or acute ischemic stroke	Yes	Binary, time-to-event	[-183,-1]	IP,OP	SNOMED	n/a	All included cohorts	n/a	n/a
Cardiovascular events	heart failure, cardiac arrhythmia, and angina will be identified.	No	Binary, time-to-event	[-183,-1]	IP,OP	SNOMED	n/a	All included cohorts	n/a	n/a
major cardiovascular events (MACE)	MACE will be identified by heart failure, acute myocardial infarction, or stroke, or the occurrence of sudden cardiac death.	No	Binary, time-to-event	[-1835,-1]	IP,OP	SNOMED	n/a	All included cohorts	n/a	n/a
pulmonary embolism		No	Binary, time-to-event	[-183,-1]	IP,OP	SNOMED	n/a	All included cohorts	n/a	n/a
deep vein thrombosis		No	Binary, time-to-event	[-183,-1]	IP,OP	SNOMED	n/a	All included cohorts	n/a	n/a
portal vein thrombosis		No	Binary, time-to-event	[-183,-1]	IP,OP	SNOMED	n/a	All included cohorts	n/a	n/a
splanchnic venous		No	Binary, time-to-event	[-183,-1]	IP,OP	SNOMED	n/a	All included cohorts	n/a	n/a

	Phase II C3-001 – Study Protocol	
	Author(s): [name], [name]	Version: v3.1
	Dissemination level: public	

thrombosis (SVT)										
cerebral venous sinus thrombosis		No	Binary, time-to-event	[-183,-1]	IP,OP	SNOMED	n/a	All included cohorts	n/a	n/a
acute myocardial infarction		No	Binary, time-to-event	[-183,-1]	IP,OP	SNOMED	n/a	All included cohorts	n/a	n/a
acute ischemic stroke		No	Binary, time-to-event	[-183,-1]	IP,OP	SNOMED	n/a	All included cohorts	n/a	n/a
stroke in general	stroke in general will include both ischemic, haemorrhagic and non-specifically recorded stroke.	No	Binary, time-to-event	[-183,-1]	IP,OP	SNOMED	n/a	All included cohorts	n/a	n/a

¹ IP = inpatient, OP = outpatient, ED = emergency department, OT = other, n/a = not applicable

² Specify whether a diagnosis code is required to be in the primary position (main reason for encounter)

8.6.3. Other covariates, including confounders, effect modifiers and other variables (where relevant)

Location at index date

For cohort 2 (Persons tested positive for SARS-CoV-2 or with a clinical diagnosis of COVID-19) and cohort 5 (Persons vaccinated against SARS-CoV2 infection) we will identify whether individuals were currently hospitalised on their index date. All people in the cohort 3 (Persons hospitalised with COVID-19) and cohort 4 (Persons requiring intensive services during a hospitalisation with COVID-19) will be hospitalised on their index date.

Demographics

Patients' age at index date and sex will be identified. Age groups will also be identified using the following groupings: <20; 20-44; 45-54; 55-64; 65-74; 75-84; ≥85 years. For those databases where such information is available, individual or area level socioeconomic status and whether they are living in the community or were a nursing home resident will also be identified.

Health conditions pre-index date

Individuals' history of the study outcomes will be identified over three time periods prior to the index date:

- 1) 30 days prior to one day prior index date,
- 2) 365 days prior to one day prior index date,
- 3) all available days observed up to one day prior to index date.

A range of health conditions, including whether a patient was immunocompromised prior to the index date, will be identified using the same time windows. Among these, the following conditions will be identified: antiphospholipid syndrome, asthma, chronic obstructive pulmonary disease, atrial fibrillation, cancer (excluding non-melanoma skin cancers), venous thromboembolism, myocardial infarction, stroke, transient ischaemic attack (TIA), heart failure, diabetes, chronic kidney disease, chronic liver disease, hypertension, rheumatoid arthritis, thrombophilia, inflammatory bowel disease (Crohn's disease or ulcerative colitis), dementia, alcohol or drug substance misuse and obesity. Venous thromboembolism, myocardial infarction and stroke are also outcomes of interest. Therefore, the number of events for venous thromboembolism, myocardial infarction and stroke in the patients history will only represent events identified prior to the washout period used to identify outcomes (section 8.6.2 and Table 6).

Medications pre-index date

Pre-existing medication use will be identified using 2 time windows, defined as 183 days to one day prior to index date, and 30 days to 1 day prior to index date. Medications of interest will be identified on the basis of Anatomical Therapeutic Chemical (ATC) codes, with use of the following medications identified:

- COVID-19 medications (ATC code: J05AB18 molnupiravir, J05AE30 nirmatrelvir ritonavir, J06BD05 sotrovimab)
- non-steroidal anti-inflammatory drugs (ATC group: M01A, with all descendant codes included)
- Cox2 inhibitors (M01AH)
- systemic corticosteroids (H02AB and H02BX), antithrombotic and anticoagulant therapies (B01A)
- lipid modifying agents (C10)
- agents acting on the renin-angiotensin system (C09)
- antineoplastic and immunomodulating agents (L)
- hormonal contraceptives for systemic use (G03A)
- tamoxifen (L02BA01)

	Phase II C3-001 – Study Protocol	
	Author(s): [name], [name]	Version: v3.1
		Dissemination level: public

- sex hormones and modulators of the genital system (G03).

Immunocompromised at the index date

People who are immunocompromised at the index date will be defined by the recording of certain conditions or certain conditions plus treatments prior to index date. People will be considered immunocompromised if they have one or more of the following conditions recorded within 365 days prior to index date:

- HIV/AIDS,
- Hematological malignancies
- Solid malignancies
- Other intrinsic immune conditions

People will be defined as being immunocompromised if they are treated with antineoplastic and immunomodulating agents between 183 days to one day prior to index date. People will also be defined as being immunocompromised if they are treated with systemic corticosteroids between 183 days to one day prior to index date and have a recording of the following within 365 days prior to index date:

- Organ transplantations
- Rheumatologic/inflammatory conditions (rheumatoid arthritis, inflammatory bowel disease, and systemic lupus erythematosus)

Smoking status pre-index date

Individuals' smoking status (current smoker, ex-smoker, or non-smoker) will be identified when available. All available history for an individual will be used to identify records of their smoking status, with the most recent record included in the analysis.

Medications on or post-index date

We will also identify medication use on or after the index date first up to 30-days. For each medication of interest, we will group users into prevalent and new users. The following medications will be identified where available: anticoagulants, anti-platelet drugs, thrombolytic agent, or transfusion with blood products or immunoglobulins, and COVID-19 medications (molnupiravir, nirmatrelvir ritonavir, sotrovimab).

Table 7. Operational Definitions of Covariates

Characteristic	Details	Type of variable	Assessment window	Care Settings ¹	Code Type	Diagnosis Position ²	Applied to study population:	Measurement characteristics / validation	Source for algorithm
Location at index date	The covid-19 hospitalized and the intensive care cohorts need to be identified in hospital setting	Binary	[0]	IP, intensive care	SNOMED	n/a	Covid-19 infected or hospitalized	N/a	n/a
Comorbidity	Check for conditions of interest at start of follow-up	Binary	All history	Primary and secondary care	SNOMED	N/A	All cohort	n/a	n/a
Medication pre-index	Check for medications exposures prior to the index date	binary	[-183,-1] [-31-1]	Primary and secondary care	ATC, RxNorm	N/A	All cohort	n/a	n/a
Immunocompromised	1.) People will be considered immunocompromised if they have one or more of the following conditions recorded in the 365 days prior to index: 
 • HIV/AIDS, • Hematological malignancies • Solid malignancies 	binary	[-365, 0] for condition, [-183,-1] for treatment	Primary and secondary care	SNOMED, ATC, RxNorm	N/A	All cohort	n/a	n/a

	Phase II C3-001 – Study Protocol	
	Author(s): [name], [name]	Version: v3.1
	Dissemination level: public	

Characteristics	Details	Type of variable	Assessment window	Care Settings ¹	Code Type	Diagnosis Position ²	Applied to study population	Measurement characteristics / validation	Source for algorithm
	
 Other intrinsic immune conditions 
2.) People will be defined as being immunocompromised if they are treated with antineoplastic and immunomodulating agents between 183 days to one day prior to index date.
 
3.) People will also be defined as being immunocompromised if they are treated with systemic corticosteroids between 183 days to one day prior to index date and have a recording of the following within 365 days prior to index date:
 
 Organ transplantations Rheumatologic/inflammatory conditions 								

	Phase II C3-001 – Study Protocol	
	Author(s): [name], [name]	Version: v3.1
	Dissemination level: public	

Characteristic	Details	Type of variable	Assessment window	Care Settings ¹	Code Type	Diagnosis Position ²	Applied to study population	Measurement characteristics / validation	Source for algorithm
Smoking status	Individuals' smoking status (current smoker, ex-smoker, or non-smoker) will be identified when available.	Binary	All records	Primary care and secondary care	SNOMED and LOINC	N/A	All cohort	n/a	n/a
Measurements	Check for measurements factors prior to the index date	Continuous	[- 12 months, 0]	Primary and secondary care	SNOMED and LOINC	N/A	All cohort	n/a	n/a
Medication during follow-up	The following medications will be identified where available: anticoagulants, anti-platelet drugs, thrombolytic agent, or transfusion with blood products or immunoglobulins, and COVID-19 medications (molnupiravir, nirmatrelvir ritonavir, sotrovimab).	Binary	[0,30]	Primary and secondary care	ATC, RxNorm	N/A	All cohort	n/a	n/a

¹ IP = inpatient, OP = outpatient, ED = emergency department, OT = other, n/a = not applicable

9 Specify whether a diagnosis code is required to be in the primary position (main reason for encounter)

